To test if two courses of treatment with a B-cell depleting antibody, ocrelizumab, corrects the B-cell tolerance defects in patients with relapsing MS.

STUDY DESIGN

DESCRIPTION OF THE STUDY

This is an open label, single-arm study of ocrelizumab in people with relapsing MS. Patients who fulfill the eligibility criteria will undergo blood draw for collection of peripheral blood mononuclear cells (PBMC). Participants will receive two infusions of ocrelizumab (300 mg) two weeks apart and then six months later (one infusion of 600 mg of ocrelizumab). Baseline MRI will be obtained 3 months after the first course of treatment. Participants will be followed with clinical visits at least twice a year (or more frequently, if needed) and brain, cervical and thoracic spine MRI, up to two and a half years after the baseline MRI.

Schedule of events. Study visits will be conducted at the Johns Hopkins Outpatient Center (JHOC). Aside from obtaining informed consent for participation in the study and collecting peripheral blood mononuclear cells (PBMCs) and the NeuroQoL, all other procedures are part of the routine clinical and standard of care at Johns Hopkins MS Center. The only deviation from the standard of care in this study is stopping the ocrelizumab infusions after two courses. Study procedures are depicted in the following table (procedures in bold font are standard of care):

Tests and	Screeni	Infusion	Month 3	Month	Month	Month	Month	Month
assessments	ng visit	visits		6	12	18	24	30

		(month	(baselin					
		0)	e)					
Informed	x							
Consent								
Verifying	X							
eligibility								
Medical history	x		x	x	x	x	x	x
Physical	Х		Х	x	х	х	х	х
examination								
and vital signs								
assessment								
Neurological	x		x	x	x	x	x	x
examination								
(EDSS)								
Blood work to	X		X	X	X			
assess eligibility								
for receiving								
ocrelizumab								
and its safety								
infusions								
infusions								
ОСТ	Х		Х		Х		Х	
Brain MRI			x		x	x	x	x
Cervical/thoraci			x		x		x	
c MRI								
NeuroQoL	x		x	x	x	x	x	x
Lymphocyte			Х	X	X	X		
subset analysis								
Blood sample	x		x	x	x	x		
collection for					.			
storage and								
future analyses								
, -								
Blood draw and	X					X (or		
collection to be						months		
sent to Dr.						24)		

[name]'s lab at Hopkins							
Ocrelizumab infusions	X 2 infusion s two weeks apart		X 1 infusio n				
Side effects assessment		x	x	x	x	x	x

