Screening visit: PI or designee will explain the study consent to study participants, and the study visit assessments will occur after the study participants sign the consent form. Screening visit procedures include review of eligibility criteria, physical exam, EDSS, collecting vitals, and blood draw (for collecting PBMCs), and completion of Neuro-QoL adult item banks. Study participants will be enrolled into the study after the study physician confirms participants' eligibility to move forward with the study.

RATIONALE FOR STUDY DESIGN

The reason we chose a single arm, open label study, as opposed to a blinded controlled study is because the latter does not help with answering our research question. Our research question is if two courses of treatment with anti-CD20 antibody, ocrelizumab corrects the B-cell tolerance defect seen in patients with relapsing-remitting multiple sclerosis.

OUTCOME MEASURES PRIMARY OUTCOME MEASURE

Assessment of T and B-cell phenotypes and function at baseline and 18-24 months post-B-cell depletion:

The assessment T and B-cell phenotypes and function and analysis of the central and peripheral B-cell tolerance checkpoints, as well as measurement of cytokines will be done at [name] at Johns Hopkins University. 50 milliliters of blood will be drawn from participants before start of the treatment with ocrelizumab (at the screening visit) and 12 or 18 months after the second course of ocrelizumab infusion (month 18 or 24 of the study) and will be sent to [name] for the analyses explained below. We will investigate the T and B-cell phenotypes in fresh blood samples from 10 individuals with MS pre-treatment and after they repopulate their peripheral B-cells likely at either 18 or 24 months' time points. We will follow the frequencies of CD3+CD4+CD25hiCD127loFOXP3+ Tregs, circulating CD3+CD4+CXCR5+PD-1+ Tfh cells increased in several autoimmune diseases, and other CD4+ and CD8+ naïve and memory T cell subpopulations. We will also assess the production of several cytokines including IL-10, IL-17, and IFN-gamma by Tregs and other T cell subsets after activating PBMCs with phorbol-12-myristate-13-acetate (PMA) and ionomycin for 4 hours in the presence of GolgiStop (BD

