We will also characterize various B-cell subpopulations in the blood of people with MS before and after treatment with ocrelizumab. We will follow the frequencies of CD19+CD10+CD27-IgMhiCD21Io transitional B-cells that recently emigrated from the bone marrow, CD19+CD10-CD27-IgM+CD21+ mature naïve B-cells, CD19+CD10-CD27+IgM+CD21+ circulating marginal zone/ IgM memory B-cells, CD19+CD10-CD27+lgM-lgG+CD21+ and CD19+CD10-CD27+lgM-lgA+CD21+ conventional lgG+ and lgA+ isotype switched B-cells as well as unconventional CD19+CD10-CD27-CD21lo CD11c+ memory B-cells that express T-bet, contain autoreactive clones and are generated after TLR activation in the presence of IFN-gamma and IL-21. The impact of anti-B-cell therapy on B-cell activation will also be determined by following CD69 expression that we previously reported to be increased on B-cells from people with MS. The expression of other B-cell activation markers such as CD80, CD86, TACI and FAS will also be assessed by flow cytometry on each B-cell subsets described above. We will also obtain a preview on the peripheral B-cell selection in MS by characterizing their proliferative homeostasis history by following the expression of proliferation marker Ki67 and using the detection of Kappa recombination excision circles (KREC) by quantitative PCR in freshly isolated B-cell subpopulations from healthy controls and people with MS before and after anti-B-cell deletion as previously described. Indeed, we previously reported that mature naïve B-cells from people with MS have undergone increased homeostatic expansion in the periphery that may result from the amplification of autoreactive clones. Altogether, these studies will determine the impact of anti-B-cell therapy on the phenotype and function of T and Bcells in people with MS.

Analysis of the peripheral B-cell tolerance checkpoints in people with MS before and after anti-B-cell therapy: We propose to assess the peripheral B-cell tolerance checkpoints in ten people with MS before and after treatment with ocrelizumab. Single CD19+CD10hiCD21-/lolgMhiCD27- new emigrant/transitional and CD19+CD10-CD21+IgM+CD27- mature naive B-cells will be isolated from the blood of these patients before and after treatment and frequencies of polyreactive, HEp-2 reactive and anti-nuclear clones will be determined as previously described. In brief, Ig heavy and light chain genes

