will be amplified by RT-PCR and 20-30 immunoglobulin genes from single new emigrant/transitional and mature naïve B-cells will be cloned and expressed in vitro. Recombinant antibodies will be tested for HEp-2 reactivity and polyreactivity by ELISAs and anti-nuclear reactivity using indirect fluorescence assay on HEp-2 slides as previously described.43 Recombinant antibodies will be considered polyreactive when they recognized all three antigens tested individually (dsDNA, insulin, and LPS) using supernatants tested at 1 μ g/ml antibody concentrations and three 1:4 dilutions in PBS as reported. In HEp-2 and polyreactivity ELISAs, ED38 recombinant antibody will be used as positive control. Hence, we will determine if B-cell depletion can correct the impaired removal of developing autoreactive B-cells in the periphery of people with MS and is associated with disease suppression.

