Anticipated results and potential pitfalls: We anticipate that B-cell depletion will correct the altered phenotype and function of T and B-cells from people with MS and normalize the production of proinflammatory cytokines in both T and B-cells. In addition, we expect that the majority of people with MS before the anti-CD20 treatment, will display a normal central B-cell tolerance with low proportions of autoreactive new emigrant/transitional B-cells similar to those in normal controls as previously reported (Figure 1A). In contrast, we anticipate that the peripheral B-cell tolerance checkpoint will be defective in MS before ocrelizumab treatment as previously reported (Figure 1B). However, we expect that mature naïve B-cells after B-cell repopulation 18-24 weeks post initial anti-CD20 treatment will show a pattern of antibody autoreactivity similar to normal controls. In other words, a short-course of treatment with an anti-CD20 antibody would correct the peripheral B-cell tolerance defect in most people with MS and this correction to be associated with long-term absence of disease activity. On the other hand, in the 3-4 people with MS who may present baseline central B-cell tolerance defect (30% in Kinnunen et al. and Figure 1A), the effects of transient B-cell depletion therapy may not be long-lasting. We may further test if a two-course treatment may induce long lasting remission through the sustained establishment of proper B cell tolerance at least in some MS patients by evaluating again their proportions of autoreactive B cells two years later (48 month time point). Although these studies are beyond the time frame of this project, the samples collected during the current proposed analysis will allow us to address this question.

Secondary Outcome Measures

Time to return of disease activity after the third month post-first-infusion, objectively demonstrated by development of new T2 hyperintense lesions or Gd-enhancing lesions on the MRI or a clinical relapse that is confirmed with an objective change in the neurological examination; proportion of patients who experience one step worsening or improvement of EDSS that is confirmed on a clinical visit six months later; Neuro-QoL in the computer-adaptive test (CAT) format before the infusions and in all the subsequent clinic visits.

SAFETY PLAN

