We will describe the demographic, clinical characteristics and MRI data of all participants before treatment with the B-cell depleting agent. Using paired t-tests, we will compare the frequency of autoreactive mature naïve B-cells, Treg and Tfh cells and cytokine production before treatment with ocrelizumab and after the B-cell repopulation. We will report the proportion of participants who experience the return of the disease activity and the time to failure event, using a Kaplan-Meyer curve. Proportion of patients with clinical relapse, new MRI activity or disability progression will separately be reported. Quality of life data will be analyzed using linear mixed effect models.

To look at the association between long-term response to B-cell depletion therapy and autoreactivity of B-cells at different stages of development, we will use logistic regression and Cox proportional hazards models with failure or time-to-failure event as the outcome variable and the above-mentioned proportion of auto-reactive B-cells at different stages of development and the change in proportions before and after treatment as the predictor variables. Failure event as defined by the return of disease activity after the third month post-first-infusion, objectively demonstrated by development of new T2 hyperintense lesions or Gd-enhancing lesions on the MRI or a clinical relapse that is confirmed with an objective change in the neurological examination or a corresponding new or enhancing lesion on the MRI that is obtained after the onset of symptoms.

Missing Data

Because of the small sample size and close follow-up, we do not expect to encounter missing data problem. Also, each participant will be his/her own control and no between-patient comparison will be made.

Determination of Sample Size

Patients' numbers are also based on our previous studies of central and peripheral B-cell checkpoints in patients with autoimmune diseases and healthy control subjects in which we had found that the frequency of autoreactive mature naïve B-cells was 48.9±3.06% in patients and 20.1±0.9% in healthy donors. Assuming that the frequency of autoreactive cells among post-treatment repopulated B-cells will be similar to normal controls, our proposed sample size of 10 subjects per group before and after

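### The objective asks whether treatment corrects the B-cell tolerance defect, but the only planned test of autoreactive cell frequency is before against after, so significance supports reduced, not corrected

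*Combined protocol and SAP*

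**What the plan says.** The Primary Objective is "To test if two courses of treatment with a B-cell depleting antibody, ocrelizumab, corrects the B-cell tolerance defects in patients with relapsing MS". Rationale for Study Design repeats it: "Our research question is if two courses of treatment with anti-CD20 antibody, ocrelizumab corrects the B-cell tolerance defect seen in patients".

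The defect is defined by comparison with healthy donors. The legend to Figure 1B describes raised proportions of mature naïve B-cells with HEp-2-binding antibodies relative to donors. Under Anticipated Results, repopulated mature naïve B-cells "will show a pattern of antibody autoreactivity similar to normal controls", and a short course "would correct the peripheral B-cell tolerance defect in most people with MS".

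The laboratory section lists three readouts: "frequencies of polyreactive, HEp-2 reactive and anti-nuclear clones will be determined as previously described". On clone numbers it says "20-30 immunoglobulin genes from single new emigrant/transitional and mature naïve B-cells will be cloned", which leaves open whether 20-30 applies to each subset or to both together.

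Statistical Methods then states: "Using paired t-tests, we will compare the frequency of autoreactive mature naïve B-cells, Treg and Tfh cells and cytokine production before treatment with ocrelizumab" versus after repopulation. The frequencies also enter "logistic regression and Cox proportional hazards models with failure or time-to-failure event as the outcome variable", but only as predictors.

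Determination of Sample Size gives 48.9±3.06% in patients and 20.1±0.9% in healthy donors, assumes that post-treatment values will resemble the donors', and claims more than 90% power with 10 subjects at a two-sided α of 0.05. Missing Data says that each participant is his or her own control and that patients will not be compared with one another.

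**The concern.** Whether a defect is corrected depends on where patients end up relative to normal. Whether it is reduced depends on how far they moved from their own baseline. The plan tests the second and asks the first. The paired test can be clearly significant while the group remains, on average, well above donors. No planned analysis of the frequency would reveal this: no reference comparison, margin or per-patient definition is given. The donor value makes full normalisation an assumption of the power calculation and is not used again.

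At stake is the main conclusion of the trial. If the donor comparison is chosen only once the data are in, its form and wording will be post hoc.

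**Working it through.** **1. The plan's own figure.** The assumed difference is 48.9 − 20.1 = 28.8 points. If ± is an SD, the pooled SD is √((3.06² + 0.9²)/2) = 2.26 and power is about 100%. If ± is a standard error from an assumed 5 to 30 subjects, the SDs are 3.06√m and 0.9√m (6.8 and 2.0 at m = 5; 16.8 and 4.9 at m = 30). Power is then at least 99.8% two-sample and 99.6% paired with zero correlation. More than 90% is confirmed as power to detect a difference under full normalisation.

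**2. How small a fall is significant.** With n = 10 the critical t is 2.262, so the smallest significant observed fall is 2.262 × SD_d/√10 = 0.715 × SD_d. The documents give no SD of paired differences. Binomial sampling alone, √(p(1−p)/k), gives 11.2 to 9.1 points at 48.9% and 9.0 to 7.3 points at 20.1% for k = 20 to 30 clones. SD_d is then about 12-14 points before any biological variation.

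| Assumed SD_d | Smallest significant fall | Share of 28.8-point gap | Post-treatment mean |
|---|---|---|---|
| 10 | 7.2 | 25% | 41.7% |
| 13 | 9.3 | 32% | 39.6% |
| 15 | 10.7 | 37% | 38.2% |
| 20 | 14.3 | 50% | 34.6% |

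**3. How often the paired test succeeds while the data show the group mean above donors.** The event is a significant paired test together with a post-treatment 95% CI wholly above 20.1%. It was simulated with 10 pairs and 48.9% before treatment. In all four rows the true mean after treatment is 34.5%, from 48.9 − 28.8/2, or equally (20.1 + 48.9)/2 for the five/five mix. The 10-15 column covers the reading that 20-30 clones are split evenly over the two subsets. The between-patient SDs are assumptions, added at each time point.

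| Scenario | 20-30 clones | 10-15 clones |
|---|---|---|
| Every patient half-corrected, binomial noise only | 72-89% | 30-55% |
| Same, plus SD 5 points | 62-79% | 25-47% |
| Same, plus SD 10 points | 36-48% | 15-27% |
| 5 normalised, 5 unchanged, binomial noise only | 26-40% | 10-18% |

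With 7 normalised and 3 unchanged, the true mean is 0.7 × 20.1 + 0.3 × 48.9 = 28.7%, and the event occurs in 12-15% of trials (20-30 clones). Reading the donor ±0.9 as a standard error and allowing for it lowers the first row by about 1 point at most.

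**4. How a CI check against 20.1% behaves.** If all patients normalise, the CI lies wholly above 20.1% in about 2% of trials. The average half-width is then 5-6 points (20-30 clones) or 7-9 points (10-15 clones) with binomial noise only. At SD 10 points it is about 8.4-9.1 points (20-30 clones). With 7 of 10 normalised, the true mean is 28.7 − 20.1 = 8.6 points above donors, yet the CI excludes 20.1% in only 16-17% of trials (20-30 clones) or 13-15% (10-15 clones).

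**The case against.** A reader might infer that the plan will declare correction on p<0.05. No section says so, and both means will be available to set beside 20.1%. That stands. The plan, however, contains nothing to prevent the inference, and the sample-size section itself moves from power for a difference to significant findings on establishing tolerance.

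A reader might also infer that the plan forbids a donor comparison. The sentence on comparing patients sits under Missing Data, donors are not trial patients, and taken literally it would bar the plan's own logistic and Cox models. Healthy controls are already named for the KREC assay. The sentence needs clarifying and is not evidence of a prohibition.

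Nor is the readout wholly undefined. The Figure 1B legend makes HEp-2 reactivity the natural reading. The sample-size paragraph does not say so, hence a request to confirm.

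The strongest objection concerns size. Uniform half-correction has no source in the documents, and the protocol expects mixed responses, with 3-4 patients in whom the effect may not last. Mixed scenarios give much lower figures, so 72-89% must not be read as the typical risk. In addition, 48.9% comes from earlier studies of patients with autoimmune diseases and is not stated to be an MS value. Finally, the proposed check is weak at n = 10 and detects little when most patients normalise. These points limit the size of the problem and the strength of the remedy. They do not supply the missing comparison.

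**Conclusion.** The concern holds and should be fixed before data are seen. The paired t-test is valid for change and its stated power is sound, but neither addresses whether the defect is corrected. A significant result would support reduced. Full correction might fit the data but would not have been tested.

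The size cannot be fixed from the documents. At a true post-treatment mean of 34.5%, a significant test with the CI wholly above the donor value occurs in 10% to 89% of simulated trials across the scenarios shown. It is frequent when patients respond uniformly and many clones are tested, and much less so when responses are mixed or clones few. These figures rest on the assumed 48.9% baseline, a fixed 20.1% reference, the clone counts and the assumed between-patient SDs. The mismatch between objective and analysis depends on none of them.

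**What to change.** 1. Keep the paired t-test and state that significance supports only a reduction.
2. Pre-specify the readout. Confirm whether 48.9% and 20.1% refer to HEp-2 reactivity and whether ± is SD or SEM. Report the post-treatment mean with its 95% CI beside the donor value and that value's uncertainty. Say that the donor value is historical and state how comparable the assays are. If the CI lies wholly above the donor value, do not claim correction of the group mean. If it includes the donor value, report not shown to differ, with the width, and do not present this as proof of correction.
3. List each patient's values before and after with clone counts, because the hypothesis concerns most patients and the mean alone cannot address that. Do not treat the donor mean as an individual normal range: with 20-30 clones, one patient's binomial standard error at 20.1% is 7.3-9.0 points.
4. Clarify that the Missing Data sentence does not bar this external reference.

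The cost is text, confirmation of a readout already measured, and a more modest conclusion. No extra samples or donors are needed. Under full normalisation the check wrongly blocks a group-mean claim in about 2% of trials. Its weakness when variation is large should be stated with the result.

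A positive claim of correction is optional and costs more. It needs a margin or per-patient definition set by the sponsor before data are seen, with its power. For illustration only, with full normalisation and n = 10, an upper 95% limit within 5 points of 20.1% is reached in 37-49% of trials with 20-30 clones and 23-30% with 10-15 (binomial noise only), and in 22-23% with 20-30 clones and SD 10 points.

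### The before/after test of mature naïve autoreactivity alone cannot separate a corrected peripheral checkpoint from a refilled B-cell pool that has not yet re-accumulated autoreactive clones

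*Combined protocol and SAP*

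**What the plan says.** All references are to the combined protocol and SAP.

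- **Question.** The section on the peripheral tolerance checkpoints says "we will determine if B-cell depletion can correct the impaired removal of developing autoreactive B-cells in the periphery". New emigrant/transitional and mature naïve cells are both cloned and tested before and after treatment.
- **Test.** Statistical Methods, by paired t-test: "we will compare the frequency of autoreactive mature naïve B-cells, Treg and Tfh cells and cytokine production before treatment with ocrelizumab" and after repopulation. Autoreactivity at different developmental stages, and its change, enters only the logistic and Cox models of clinical failure. KREC and Ki67 are measured at both times but do not appear in that section.
- **Mechanism.** The background describes the MS defect as a build-up of autoreactive mature naïve cells. The primary outcome section adds that "mature naïve B-cells from people with MS have undergone increased homeostatic expansion in the periphery that may result from the amplification of autoreactive clones". New emigrant cells are expected to look normal in most patients, but no frequency is given for them.
- **Sampling.** There is one post-treatment draw, "12 or 18 months after the second course of ocrelizumab infusion (month 18 or 24 of the study"), taken "after they repopulate their peripheral B-cells likely at either 18 or 24 months' time points". No repopulation threshold or minimum time since repopulation is set. Lymphocyte subsets are scheduled at months 3, 6, 12 and 18, but not at month 24.
- **Interpretation.** Anticipated results and potential pitfalls treats a healthy-like mature naïve pattern after repopulation as correction. It gives the timing as "18-24 weeks post initial anti-CD20 treatment". It mentions a possible look at month 48, outside the project, and says "the samples collected during the current proposed analysis will allow us to address this question".

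**The concern.** Removal is what happens between the new emigrant and the mature naïve stage. The planned test looks only at the output of that step. Depletion empties the mature naïve pool and largely normal new emigrants refill it. On the protocol's own account of how autoreactive clones build up, a young pool may contain few of them even when removal is as faulty as before. Both explanations predict a lower mature naïve frequency than at baseline, so a significant paired test does not choose between them. At stake is the meaning of a positive result on the primary objective.

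**Working it through.** **1. The plan's own figure.** Determination of Sample Size gives 48.9±3.06% in patients and 20.1±0.9% in healthy donors, with 10 subjects, two-sided 0.05 and power above 90%.

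- Difference: 48.9 − 20.1 = 28.8 points.
- Reading ± as SD: pooled SD = √[(3.06² + 0.9²)/2] = 2.26, standardised effect 28.8/2.26 = 12.8, power about 100%.
- Reading ± as SEM from an assumed 25 donors: SDs 15.3 and 4.5, pooled 11.3, two-sample power still at least 99.9%.

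The figure reproduces. It is power for a fall from any cause.

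**2. The planned test when nothing is removed.** Assume that refilled mature naïve cells mirror the new emigrant pool at level p. The documents give no MS new emigrant frequency, so p = 25% to 40% is an assumed range. The SD of the paired difference is assumed to be 11.7 to 14.3 points. This matches binomial noise for 48.9% against 20.1% with 30 and 20 clones: √(9.13² + 7.32²) = 11.7 and √(11.18² + 8.96²) = 14.3. Between-patient variation in the change would widen it and lower the probabilities below.

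λ = (48.9 − p)·√10 / SD. Probability = P(noncentral t with 9 df > 2.262).

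| p | Fall (points) | λ at SD 11.7 / 14.3 | Probability significant |
|---|---|---|---|
| 25% | 23.9 | 6.46 / 5.29 | >99% / >99% |
| 30% | 18.9 | 5.11 / 4.18 | 99% / 96% |
| 35% | 13.9 | 3.76 / 3.07 | 92% / 78% |
| 40% | 8.9 | 2.41 / 1.97 | 57% / 42% |

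**3. Why time since repopulation matters.** As an illustration only, let an unchanged defect rebuild exponentially from 20.1% towards 48.9% (25 clones, between-patient SD 6 points, simulated). Six months after repopulation the paired test is significant in about 45%, 86% or 98% of trials for assumed time constants of 6, 12 or 24 months. At 12 months after repopulation the figures are 10%, 46% and 87%. The documents give no rate.

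**4. The before/after change in the step does not help.** Under a reset, new emigrants stay at p while mature naïve cells fall from 48.9 to p. The change in (mature naïve − new emigrant) is (p − p) − (48.9 − p) = −(48.9 − p), the same as the mature naïve change alone. With 25 clones per compartment and assay noise only, the SD is √[(48.9×51.1 + 3p(100 − p))/25]. At p = 25 this is 18.0, λ = 23.9×√10/18.0 = 4.19, and the probability is 96%. At 30%, 35% and 40% it is 81%, 53% and 25%.

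**5. The post-treatment step on its own does help.** Under a reset the expected difference is zero. Under working removal, mature naïve frequency is lower than new emigrant frequency in the same sample. With 25 clones per compartment and assay noise only:

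- 35% to 20%: SD = √[(35×65 + 20×80)/25] = 12.4, SE = 12.4/√10 = 3.9, λ = 3.81, power about 92%.
- 25% to 20%: SD = √[(25×75 + 20×80)/25] = 11.8, SE = 3.7, λ = 1.34, power about 22%.
- 40% to 20%: SE = 4.0.

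The protocol plans 20-30 antibodies and does not say whether that is per compartment. If it is the total over both, the noise is larger.

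**The case against.** The opposing case has several sound parts.

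- **Timing.** A reader might infer that the sample catches B-cells just as they return. The text does not say so. The draw is 12 or 18 months after the second course, and a patient repopulated by month 12 would be sampled at least six months later. What stands is that the interval is not fixed and not analysed.
- **Other evidence.** A reader might infer that mature naïve frequency is all that is tested. Treg, Tfh and cytokines are in the same sentence, and Treg suppressive function is measured before and after. The protocol links the peripheral checkpoint to Treg function, so these results bear on the question. They are indirect, and no before/after analysis uses the removal step.
- **Criterion.** The plan expects a healthy-like pattern, not merely p<0.05 against baseline. With 25 clones and n=10, means of 30%, 35% and 40% lie 3.4, 4.9 and 6.4 SE above 20.1%, and would not look healthy. Only 25% (1.8 SE) is ambiguous. This is fair, but no formal comparison with controls is planned, so the planned test gives no protection.
- **Durability.** The protocol openly places sustained tolerance outside the project. Its remark on collected samples can be read as meaning that they serve as comparators for a later draw. It is loose, not clearly false.

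**Conclusion.** The concern holds as a limit on interpretation. A significant fall in mature naïve frequency could be a reset and not a correction, and the planned before/after test does not tell them apart. With no removal at an assumed 25% to 40%, the chance of a significant result runs from above 99% down to 42-57%. That rests on the assumed levels and on an SD of differences of 11.7 to 14.3 points.

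It would go too far to say that the trial will misread a reset as correction: no re-accumulation rate is given. The stated power is not in dispute. The gap is mainly one of analysis, since the data that discriminate are already to be generated. Even a clear post-treatment fall between stages would show removal operating at that draw, not lasting tolerance.

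**What to change.** 1. Keep the planned paired test. Add a pre-specified within-patient comparison of new emigrant and mature naïve autoreactive frequency in the post-treatment sample. Name one reactivity assay and use it for both stages: the background figure legend describes polyreactivity for new emigrants and HEp-2 reactivity for mature naïve cells. Report an estimate with a confidence interval, next to the same quantity at baseline. Do not make the before/after change in this step the deciding measure.
2. Report KREC, Ki67 and time since B-cell return beside it, taking the last from the scheduled lymphocyte subsets. For patients drawn at month 24, return can only be placed between visits.
3. If no post-treatment fall from new emigrant to mature naïve is shown, limit the conclusion to lower autoreactivity after repopulation and do not claim a corrected checkpoint.
4. Reconcile the timing in weeks under Anticipated results with the timing in months under the primary outcome. Reword the 48-month remark to say that the collected samples can only be comparators for a later draw.

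Cost: items 1 to 3 need analysis wording and no new samples; item 4 is text. The added comparison has an SE of about 3.7 to 4.0 points from assay noise alone, and more with between-patient variation. Power is about 92% for a 35% to 20% fall but about 22% for 25% to 20%, so an absent fall is inconclusive when new emigrant frequency is low and should be reported as such.
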